3.5.3 Exploratory outcomes

- Quantitative measures of airway geometry and densitometry (Weeks 0 and 48, noncontrast thoracic CT-derived outcomes)
 - MLD E/I (small airway)
 - % WA
 - LA (larger airways)
- Mediators
 - Sputum mediator profiling (biomarkers)
 - Blood biomarkers
- Cell subset analysis including but not restricted to exploration of ILC2 cells
- Urine biomarkers of inflammation
- Mediator profiling (biomarkers)
- Upper airway inflammation:
 - nasosorption
 - nasal epithelial sampling (optional)
- Airway infection and ecology:

- targeted qPCR (bacteria and viruses) for common airway pathogens
- microbiomics
- Breath volatile organic compound (VOC) profiling (PTR-MS & ADVION) breathomics
- Pharmacogenomics response analysis in subgroups determined by SNPs for alleles associated with the IL33/ST2 axis

4 TRIAL DESIGN

This is a single-centre, double-blind, placebo- controlled, parallel group, randomised controlled trial to assess the efficacy and safety of anti-ST2 compared to placebo, in patients with moderate to very severe COPD (GOLD II-IV). Anti-ST2 will be administered via subcutaneous injection once every 4 weeks (Week 0, 4, 8, 12, 16, 20, 24, 28, 32, 36, 40, and 44) during the 48-week treatment period. The treatment period will be followed by a 12-week follow-up period (i.e washout period). An overview of the trial design is presented in Figure 1.

After signing the informed consent at the initial visit, patients will enter a screening period within 7-14 days of randomisation. Patients who qualify to participate in the trial will be randomised into a 48-week treatment period in which they will receive either 490 mg anti-ST2 or a matching placebo. Patients will be evaluated for an additional 12 weeks following completion of the efficacy endpoint (visit 13, week 48). Treatment groups will remain blinded until the 60-week follow-up period is completed, and trial database is locked. Visit procedures will be performed as shown in Appendix 1.

5 TRIAL SETTING

This trial will be a single centre RCT, sponsored by the University of Leicester and coordinated by the Leicester NIHR Respiratory BRC and Leicester Clinical Trials (LCTU).

6 PARTICIPANT ELIGIBILITY CRITERIA

Eligibility criteria for this trial have been carefully considered to ensure the safety of the patients included in the trial and that the results of the trial can be used. It is important the participants meet all the inclusion criteria and none of the exclusion criteria.

6.1 Inclusion criteria

- 1. Symptoms typical of COPD when stable (baseline mMRC dyspnoea score \geq 2)
- 2. GOLD COPD stage 2-4
- 3. Smoking pack years \geq 10 years
- 4. Age > 40 years
- 5. Receiving standard-of-care drug therapy as per BTS guidance for COPD
- 6. A history of \geq 2 moderate-to-severe exacerbations in the last 12 months.
- 7. Be able to give valid written consent; compliant with trial procedures and trial visits.
- 8. Able to understand written and spoken English.

6.2 Exclusion criteria

- 1. Significant known respiratory disorders other than COPD that in the view of the investigator will affect the trial
- 2. Patients whose treatment is considered palliative (life expectancy <12 months)
- 3. Known hypersensitivity to the active substance of IMP or any of the excipients
- 4. Known history of anaphylaxis
- 5. Patients with a COPD exacerbation and/or pneumonia within the 4 weeks prior to visit 1
- 6. Have, in the opinion of investigator, uncontrolled co-morbid conditions, such as diabetes mellitus, hypertension and heart failure [e.g. NYHA class III (e.g. less than ordinary activity causes fatigue, palpitation, or dyspnoea) patients will be excluded if they have had exacerbation of their HF in previous 6 months, and class IV (e.g. Symptoms of heart failure at rest)] that will affect the trial.
- 7. Myocardial infarction, unstable angina or stroke within 12 month prior to screening
- 8. Diagnosis of malignancy within 5 years of visit 1 (except for excised localised carcinoma of skin not including malignant melanoma)
- 9. Clinically significant ECG changes, which in the opinion of investigator warrants further investigations
- 10. Laboratory abnormalities, which in the opinion of investigator warrants further investigations
- 11. Have, in the opinion of the investigator, evidence of alcohol, drug or solvent abuse.
- 12. Pregnant, breastfeeding, or lactating women. Women of child-bearing potential (see protocol section 9.7)) must have a negative blood serum pregnancy test performed at the screening visit and must agree to use two methods of birth control, (one of which must be a barrier method).
- 13. Participation in an interventional clinical trial within 3 months of visit 1 or receipt of any investigational medicinal product within 3 months or 5 half-lives.
- 14. Upon questioning the patient has blood born infection (e.g. HIV, hepatitis B or C).

7 TRIAL PROCEDURES

See appendix 1 for detailed visit structure and trial procedures.

7.1 Participant Identification and Recruitment

The trial will recruit in a single centre (NIHR Leicester BRC Respiratory) that has a previous track record of delivering randomised designed studies. The participants will be identified from a database which has the details of patients who have taken part in previous COPD related trials and have consented to be contacted for future trials. They will also be identified from respiratory outpatient clinics and acute admission unit.

We will recruit members of the public who self-refer and who meet the inclusion/exclusion criteria. We will put posters advertising the study throughout the University Hospitals of Leicester NHS Trust and with permission in other community settings such as, pharmacies, GP practices and public notice boards. We will also make use of the NHS intranet, digital and social media (such as Facebook and Twitter) to help promote the study, whilst interest and patient feedback regarding the study will be generated via other media outlets (e.g. press releases, radio) where possible.

Patients will also be recruited from primary care. The Clinical Research Network (CRN) East Midlands will assist with identifying GP practices that are willing to identify potential participants for the trial. The practice will identify potential participants from the practice database for eligibility based on criteria supplied by the research team. Additionally, posters will be placed in the practice and clinical rooms, alerting staff and patients to the trial. The practice team will invite the patient to participate and the patient will respond to the research team if they wish to do so. Although this is a single centre trial, participants will be recruited from GP practices across Leicester, Leicestershire, Rutland (LLR) Clinical Commissioning Groups (CCGs).Once a participant has been identified as potentially eligible or requests further information, they will be sent a letter inviting them to express interest in the trial and return a reply slip which will contain the minimum amount of personal data. Alternatively they will be approached by a member of the clinical or research team and if interested their details passed onto the trial team for eligibility assessment. The trial team will contact the participant and arrange for a baseline screening visit (visit 0) and advise the participant to bring any concurrent medications with them.

They may also discuss halting any current medication such as inhalers that would affect the baseline measures. For participants with long acting inhalers, i.e. taken once a day (e.g. Spiriva) we would recommend these be halted 24 hours before the visit. For medium acting inhalers i.e. taken twice a day (e.g. symbicort, seretide, fostair, eklira, Anoro ellipta, Duaklir genuair, and Duoresp spiromax), we would recommend halting 12 hours before the visit. All other inhalers we would recommend halting 4 hours before the visit. This information would also be stated in the letter generated by the trial team with the appointment details.

Eligible participants will be offered trial entry at the baseline screening visit (visit 0) after they have had 24 hours to read the PIS and have understood the nature of trial.

7.1.2 Screening

Each potential participant will provide informed consent at screening before starting any trial related procedures. Participants will be assessed for eligibility as per inclusion/exclusion criteria at initial screening and at each subsequent follow up visit this will be checked for changes.

All potential participants who submit a reply or who agree to be contacted by the trial team, will be assigned a screening number and will be reviewed by a member of the research team who will screen for eligibility using pre-specified inclusion/exclusion criteria prior to or at the consent/screening visit. Participants who are deemed not to be eligible for the trial (even if this is prior to a screening visit 0), will be screen failed and their anonymised data (initials and year of birth) added to the screening log along with the details of their ineligibility. This will be maintained by the blinded trial staff with the Investigator Site File (ISF).

A log of all participants enrolled in the trial (i.e. who have been randomised) will also be created and kept securely with the unblinded staff as it will contain the treatment information.

7.1.3 Payment

Participants will be reimbursed for travel expenses at the usual NHS Trust rate (up to a maximum of £50 per visit) payable on production of original receipts (if taxis are not provided) at all trial visits (including screening and exacerbation visits). Once randomised participants will

Page **17** of **60**

receive an additional £25 per completed scheduled visit to compensate for any inconvenience. The payment schedule will depend on the participant's preference and will either be received after a series of visits have been completed, or at their final visit in a single lump sum.

7.2 Consent

Written version of the participant information sheet and consent form will be presented to the participants detailing the exact nature of the trial; what it will involve for the participant; the implication and constraints of the protocol; the potential side effects and any risks involved in taking part. It will be clearly stated that the participant is free to withdraw from the trial at any time for any reason, without prejudice to future care, and with no obligation to give the reason for withdrawal.

The participant will be given a minimum of 24 hours to consider the information and have the opportunity to question the researcher, or other independent parties to decide whether they will participate in the trial. The participant will attend an initial screening visit, where written informed consent will then be obtained by means of participant dated signature and dated signature of the person who presented and obtained the informed consent, which will contain information that conforms to current data sharing and handling requirements.

7.3 Blinding

Participants, investigators, the Trial management team and everyone involved in trial conduct will remain blinded with regard to the randomised treatment assignments until after database lock.

Unblinded personnel will include:

- The trial statistician, in order for the unblinded DSMC to make safety decisions
- The Pharmacy team, to take receipt of and dispense the IMP/placebo
- The designated individuals from the Respiratory BRC responsible for reconstituting the IMP/placebo.
- The trial monitor, in order to perform drug accountability and reconciliation. The Sponsor and the trial monitor are one entity; therefore it will not be possible to maintain the blind of the Sponsor.

The IMP and placebo will be shipped by Genentech to the Hospital Pharmacy. Genentech will be responsible for QP release and the trial drug will arrive unblinded, pre-labelled with the approved trial outer labels. The entire Pharmacy team are unblinded and will take receipt of the IMP and placebo in accordance with their local SOPs and complete the necessary documentation including the accountability logs which will be maintained securely in the trial Pharmacy Site File. They will provide the IMP/placebo to the unblinded trial personnel only. The Unblinded trial personnel will collect and transfer the unprepared IMP/Placebo making sure that they are not visible to anyone during transport i.e. transferred in a closed non-transparent bag.

The unblinded trial personnel are designated in the Delegation Log and will be responsible for randomisation and trial drug preparation and reconstitution, which will take place in Glenfield out of sight of blinded trial personnel or the participant with clear warning notices that unblinded

IMP is being prepared. All documentation of drug/placebo preparation (including a participant accountability log), randomisation CRF, prescription, and the enrolment log containing information about randomisation for each participant, will be kept in a folder in a sealed box and location will be unknown to blinded team. A yellow label will be added directly to the syringe containing only the participant ID, initials, a statement that it is 'either drug or placebo within', date, time of preparation, and the initials of the unblinded personnel preparing it.

This 'blinded yellow label syringe' will be given to a Blinded trial personnel to be administered to the participant on site. The IMP and placebo will be identical in physical appearance within the syringe.

The randomisation results will not be revealed until the Clinical Trial Unit perform final database lock.

A DSMC will be reviewing the trial data periodically, to assess patient safety and will have access to unblinded data if necessary as outlined and agreed in the DSMC Charter. Data presented at the DSMC will be prepared by the unblinded trial statistician and take the format of an open blinded session followed by a closed unblinded session (as appropriate) to prevent unblinding of the CI, trial manager and the rest of the trial team.

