The trial sponsor, University of Leicester, will be responsible for all aspects of the trial as per ICH-GCP, apart from where these duties have been delegated to the Leicester Clinical Trials Unit. The funder, Genentech, will be responsible for funding the trial, supplying the drug and placebo, performing certain sample analysis not available at Leicester. Data and samples will be shared between the Sponsor and Funder and the Funder will be provided with all Protocols and SOPs for their comment and input.

vi. ROLES AND RESPONSIBILITIES OF TRIAL MANAGEMENT COMMITEES/GROUPS & INDIVIDUALS

Trial Management Committees

The TMG will comprise of the trial Chief Investigator, Trial Clinical Co-ordinators, Trial Manager, Database Developer (as required), Trial Statistician and a Research Nurse. The TMG will be responsible for the day-to-day management of the trial. The TMG is responsible for all aspects of the trial (including recruitment rate, budget management, safety reporting, protocol compliance etc.) and for ensuring appropriate action is taken to safeguard trial participants and the quality of the trial.

Trial Steering Committee (TSC)

The TSC will comprise of an Independent Chairperson, Chief Investigator, Funder Representative and other Independent Members including Patient Representative. The TSC will provide oversight of the trial and monitor the progress of the trial to ensure it is being conducted in accordance with the protocol, relevant regulations and the principles of GCP.

Data Safety Management Committee (DSMC)

The DSMC will consist of independent experts who will assess the progress, conduct, participant safety and critical endpoints of a clinical trial. The DSMC will adopt a DAMOCLES charter to define its terms of reference and operation and will make recommendations to the TSC. The DSMC will meet on a regular basis as specified in the DSMC charter to review the

Page 9 of 60

trial information and accruing data during the conduct of the trial and make recommendations to the TSC.

vii. Protocol contributors

- [name] and [name], Respiratory BRC- trial design and protocol write up.
- [name], [name] and [name], Leicester Clinical Trials Unit sample size, statistical analysis & randomisation.
- [name] and [name], Leicester Clinical Trials Unit trial management, safety reporting & pharmacovigilance, randomisation, data management, quality assurance.

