10.10 Interim analysis and criteria for the premature termination of the trial

There will be no interim analysis or formal criteria for the premature termination of the trial.

The DSMC will receive reports on the safety and other outcomes every 3-6 months (as defined in the charter), with their main focus being to ensure the safety of the trial. DSMC report will

report AEs, SAEs, demographics and efficacy outcomes. The open session of the DSMC will only report data overall, not split by arm. Outcome data will be restricted to the closed report.

There will not be any formal test or criteria for early stopping of the trial. The DSMC will advise on stopping the trial only if the acquired data provides proof that would alter current clinical management, in the light of the observed data and any other published literature.

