# 4.3 Interim Analysis and Data Review

There is no interim analysis planned. The DSMC will receive report three monthly during recruitment period, then six monthly thereafter during 12 month follow-up period. The report will contain tables on recruitment, disposition of participants, trial and data quality, adverse events, and protocol deviations. There will be open and closed sessions. The open sessions will involve presentation of data relating to recruitment and retention based on pooled data and data quality (e.g data return dates, treatment compliance) blind to treatment allocation. The closed session will involve presentation of efficacy and safety data unblinded by treatment group.

Recruitment and disposition will also be presented in a Consolidated Standards of Reporting Trials (CONSORT) diagram.

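### The unblinded trial statistician sits on the TMG that Protocol 7.3 treats as blinded, and no stated separation keeps by-arm efficacy away from the SAP's authors

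*Protocol*

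**What the plan says.** Protocol section vi sets the TMG's membership: "The TMG will comprise of the trial Chief Investigator, Trial Clinical Co-ordinators, Trial Manager, Database Developer (as required), Trial Statistician and a Research Nurse". It makes the group responsible for the trial as a whole.

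Protocol 7.3 opens with a general rule, to hold until after database lock: "Participants, investigators, the Trial management team and everyone involved in trial conduct will remain blinded". A list of unblinded personnel follows, and its first entry is "The trial statistician, in order for the unblinded DSMC to make safety decisions". SAP 1.2.5 repeats both the rule and the list.

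Protocol 7.3 then assigns the reporting task: "Data presented at the DSMC will be prepared by the unblinded trial statistician". Protocol 10.10 says the DSMC report will "report AEs, SAEs, demographics and efficacy outcomes", with outcome data kept to the closed report. SAP 4.3 is explicit: "The closed session will involve presentation of efficacy and safety data unblinded by treatment group". It sets reports at three-monthly intervals during recruitment and six-monthly during follow-up.

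Protocol 10.3 has the SAP prepared early but finalised at any time before lock. Protocol section vii credits three contributors with "Leicester Clinical Trials Unit sample size, statistical analysis & randomisation".

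**The concern.** An analysis plan is persuasive as prespecified when the people writing it could not have known how the arms compared. Here the only statistical role that the documents name as unblinded has regular sight of efficacy by arm. It also has a seat in the group that runs the trial, while the SAP is still open. The open and closed DSMC sessions are described as protecting the chief investigator, the trial manager and the rest of the team. They are not described as protecting the plan.

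At stake is the sponsor's ability to show, from its own documents, that late decisions were made without knowledge of results. This matters most for parts of the plan that the protocol leaves to the SAP: subgroup definitions, the choice of outcomes for per-protocol analysis, the imputation settings and the secondary-outcome methods.

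**Working it through.** The documents give no figure to reproduce for this point. The check traces the role, then the timing, then what remained open.

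**1. Role.** Reading the trial management team of 7.3 as the TMG of section vi (an assumption, though the natural one):

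- TMG member: yes (Protocol vi).
- Blinded as part of the management team: yes, under the general rule of 7.3.
- Unblinded: yes, under the list in 7.3 and SAP 1.2.5.
- Sees efficacy by arm: yes (Protocol 7.3 and 10.10, SAP 4.3).
- Barred from TMG business, protocol amendments or SAP drafting: not stated anywhere.

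**2. Timing.** The protocol's amendment history (NSA01) refers to an agreement of 11 September 2019 under which all participants had been recruited. The SAP history runs from v0.1 (15 October 2018) to v2.0 (18 August 2020), the first version labelled as signed off. It includes a subgroup clarification in v1.2 (27 July 2020). From 11 September 2019 to 18 August 2020 is about 11 months. On a six-monthly schedule at least one report falls due in that gap, in addition to the three-monthly reports during recruitment. This shows what was scheduled, not what was delivered.

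**3. What the open SAP could still affect.**

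- Primary model family, covariate and ITT population: fixed in Protocol 10.5 and 10.11.
- Deviations: the major types are listed in SAP 3.1.1 and affect only the per-protocol analysis (SAP 5.4.2).
- Controlled imputation without a scenario or parameters (SAP 5.4.3): a sensitivity analysis only.
- Log transformation or rank test without criteria (SAP 5.5.1): secondary outcomes only.
- Poisson fallback if the dispersion is non-significant, with no test or level named (SAP 5.4.1): this bears on the primary result. It depends on fitting the primary model, so the decision is made after lock.

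**4. Size of the Poisson fallback.** This was simulated under no treatment effect with n = 36 per arm (80 × 0.9 / 2), a mean count of 2, no covariate, 4,000 replicates, and a 5% likelihood-ratio test of dispersion (level assumed). The Wald statistic is log(m1/m0) / √[(1/m0 + 1/m1 + 2k)/n], where m0 and m1 are the arm means and k is the estimated dispersion. Poisson sets k = 0. The plan's 1.3 does not say which parameterisation is meant, so true k was varied: 1.3; 1/1.3 = 0.769; 0.3; and 0.3/2.85 = 0.105 (1.3 read as variance over mean at 2.85).

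| True k | Dispersion significant | NB error | Poisson error | Rule as written |
|---|---|---|---|---|
| 1.3 | 100% | 6.2% | 30.4% | 6.2% |
| 0.769 | 99.8% | 6.4% | 22.1% | 6.4% |
| 0.3 | 80.2% | 6.3% | 12.3% | 6.7% |
| 0.105 | 23.9% | 5.5% | 7.4% | 6.6% |

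The rule applied mechanically adds 0, 0, 0.4 and 1.1 percentage points to the negative binomial error. The simulation error is about √(0.06 × 0.94 / 4000) = 0.4 points. Poisson alone would be seriously anti-conservative with real overdispersion, but the SAP's condition almost never permits it there. What remains is loose wording, with no test and no threshold.

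**The case against.** Section 7.3 states a general rule and then names exceptions, and the statistician is one of them. On that reading the text is not self-contradictory and the TMG list only needs a cross-reference. This stands in part: the exception explains why the statistician is unblinded. It does not explain how an unblinded member takes part in a group described as blinded, because no recusal is stated.

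The SAP author may well have been blinded. Author names are removed, three CTU contributors are listed, several people reviewed the SAP, and the DSMC charter is not available. Protocol 7.3 also makes DSMC access to unblinded data conditional on need, as the charter sets out. All of this stands. The finding is that these documents state no separation, not that none existed.

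A reader might infer that protocol v7.0 moved subgroup objectives to exploratory status because of results. The amendment history gives external reasons: COVID-19 limits on shipping and laboratory work, and missed CT scans. The change also narrows the claims. Likewise, the 300 cells/µL cut-off and the SGRQ-c domains added after lock are openly labelled post hoc.

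A firewall before lock would not govern the dispersion and normality decisions, which are taken at final analysis. This stands, and is why the Poisson clause needs its own remedy.

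**Conclusion.** The point holds as a missing safeguard that should be put right. As written, an unblinded statistician with scheduled access to by-arm efficacy sits on the TMG while the SAP can still change, and nothing stated keeps that knowledge from the SAP or from TMG decisions.

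Its size cannot be given as a number. A reader might infer that informed choice among several analyses could carry the primary p-value across 0.05, and might price this as a choice among correlated specifications. The documents identify no such set of primary analyses. The model family, covariate and population are fixed in the protocol, and the Poisson rule as written adds about 0 to 1 point of type I error in the simplified simulation. The exposure lies mainly in secondary, sensitivity, subgroup and per-protocol analyses and in TMG decisions.

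The conclusion assumes that the trial management team of 7.3 is the TMG and that closed reports followed the stated schedule. A record showing that the SAP author had no by-arm access would settle the question for the versions already written.

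**What to change.** In Protocol vi and 7.3, and in SAP 1.2.5 and 4.3, state that:

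- the statistician who prepares closed DSMC reports is not a TMG member and, before lock, does not draft, amend or sign the protocol or SAP, or classify deviations;
- another statistician from the existing CTU team, without access to closed reports, holds the TMG seat and owns the SAP until lock.

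For SAP versions already written, disclose whether the author had by-arm access at the time.

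In SAP 5.4.1, delete the Poisson option and keep the protocol's negative binomial model as the primary analysis whatever the dispersion estimate. This removes a choice made after lock that a division of staff would not control.

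The cost is a re-division of duties and a handover between two existing statisticians. Sample size, visits and endpoints are unchanged.
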